## **6.2 The Statistical Analysis Plan**

### ***6.2.1 Efficacy population***

To analyze the efficacy, we will apply by “Intention to treat (ITT)” analysis.

### ***6.2.2 Immunogenicity population***

To evaluate the vaccine immunogenicity, we will use a PP analysis, through which the immunogenicity indicators, i.e., seroconversion and neutralization, will be measured in those subjects receiving all vaccine doses and compared with the placebo group.

### ***6.2.3 Safety population***

We will benefit from a “per-protocol (PP)” analysis to evaluate vaccine safety. In this approach, the solicited and unsolicited adverse events will be determined and compared between those subjects receiving at least one dose of vaccine and those receiving at least one dose of placebo.

### ***6.2.4 Subgroups analyses***

Vaccine Efficacy will be calculated among different subgroups of gender (Male and Female), ages (under and above 65), and underlying diseases (yes and no) using stratified Cox regression and logistic model for long format dataset using a working correlation matrix.

### ***6.2.5 Analysis of efficacy***

Considering the high incidence of COVID-19 in Iran and the high sample size of the study, the duration of follow-up for the efficacy analysis in C1 is estimated to be four months (3 months after the second dose) making it possible to estimate the efficacy with a significance level of  $\alpha$

<0.0001. The study duration for safety analysis in C1 is six months. Also, the duration of follow-up for the efficacy analysis in C2 is estimated to be six months (4 months after the third dose). Such a duration brings a possibility to estimate the efficacy with a significance level of  $\alpha < 0.0001$ . The study duration for side effect analysis in C2 will be seven months (or five months after the third dose).

### **6.3 Statistical tests**

We will apply the stratified Cox regression model to estimate vaccine efficacy. The efficacy will be reported using the “1-Hazard Ratio”. Also, vaccine efficacy will be estimated through a logistic regression on the long person-time format dataset using a working correlation matrix. In this model, the efficacy will be reported using the “1-OR”.

In each study arm (placebo vs. treatment), the frequency of adverse reactions or events will be described and estimated with 95% CI. The seroconversion frequency (cases with a four-fold rise in S antibody titer compared to the base) will also be described with 95% CI in each study arm. Furthermore, the geometric mean of the antibody titer will be calculated and reported with a 95% CI. Antibody titers between the vaccine and placebo groups will be compared with Mann-Whitney U. Also mean difference and the mean ratio will be calculated. The frequency of serious and unsolicited adverse events will be separately described and categorized system-by-system. The affected body systems are based on the classification in the “Medical Dictionary for Regulatory Activities” (MedDRA). All statistical analyses will be performed with R and Stata software (v. 16).

### **6.4 Working group for statistical analyses**

In this RCT, an independent team will do data gathering, data cleaning, statistical analyses and interpretation of results. The members of that working group are affiliated with the Kerman University of Medical Sciences. The team consists of Bio-statisticians and Epidemiologists.

### **6.5 Data Gathering Methods**

Data collection will be through electronic forms. Co-PIs in 8 cities are in charge of supervision of data collection. Research data will be collected and managed via a web-based platform developed by an Iranian knowledge-based company titled “Vista idea builders in Technology.” This company supports the platform as well.

Each recruitment and vaccination site has its access level, which is separated from the other cities and enables operators to enter data, CoPIs to ask for data editions, and the PI to approve editions. The platform helps PI and sponsors monitor the RCT progress and make reports for DSMB and steering committees. The volunteer records its adverse events in the AEs report form till three days after each dose and hands it over to one of the designated physicians at the vaccination site. Also, it is possible to report AEs telephonically or to a designated hospital in person, which will be recorded with the volunteer's UUID in eCRF.

## **6.6 Data management**

The PI is accountable for holding all forms and documents related to study participants during the study. After the study, all forms and documents will be submitted to the data management center at the PI's request. One copy of documents can be maintained in each study center at CoPI demand. All confidentiality principles will be followed in submitting and receiving all documents.

## **6.7 Data monitoring plan**

As a part of the GCP of this RCT, the monitoring team will monitor the implementation, recording and reporting of the study periodically.

### ***6.7.1 Monitoring Team Visits***

**6.7.1.1 Pre-trial Monitoring:** The monitoring team visits each city 2-7 days before the initiation of its vaccination site activity. The visit aims to assess the capabilities of the visited city to start the study, e.g., sufficient vaccine supply, necessary documents and equipment, investigators and staff and their knowledge.

**6.7.1.2 Trial Initiation Visits:** Will be held one day before the initiation, and processes fluency will be checked, and necessary feedback for improvements will be provided. On the following day, the vaccination site will be officially inaugurated during a ceremony with influential figures in the city. Such a design guarantees community engagement. On the first day, the monitoring team continues to provide feedback to the site staff and address questions or any remaining gaps.

**6.7.1.3 Routine Monitoring Visits:** The monitoring team will visit each city at least twice during the study period in a one-month interval. The objective is to make sure the accuracy of the implementation phase is based on GCP standards.

**6.7.1.4 Close-out Visit:** At the end of the study in each city (3 months after the last vaccine dose), a visit will be considered to ensure an accurate archive of documents, return of study products, equipment and others.

## **6.8 Criteria to conclude the study**

In case the following criteria are met, the study can be concluded:

- All serologic studies are performed according to timetable and test results are reported
- All volunteers' visits are done and related documents are delivered to the PI and archived
- All remaining vials are counted and given back to the sponsor
- The final study report is written

## **7. Inspection and auditing**

As a component to establish a quality assurance process, Pasteur Institute of Iran has considered the auditing process. Auditing the study will be done by an independent person selected by the sponsor and will visit the designated cities and vaccination sites monthly without any advance notice. The purpose of the sponsor's audit is independent assessments of all activities, logistics and documents of the study to ensure that those are well corresponding with the study protocol. The audit reports are submitted to the primary research team and the sponsor.

### **7.1 The Auditor's Visits**

1- **The scheduled visits:** The auditing team will visit study sites before the study and at monthly intervals during the study, so they guide the implementers and provide feedback to diminish possible errors and any diversion from the protocol.

2- **Ad hoc visits for specific reasons:** In case of any SAE or any report of serious issues in quality implementation in one or several vaccination sites, the auditor will visit those sites at the sponsor's request.

**Box 1. Classification of Recruiting Cities Based on the Number of Doses and Laboratory Assays**

**C1: Two-dose of SOBERANA-02 (days 0 & 28):** We will recruit a total sample size of 18,000 volunteers in Six cities of **Babol, Sari, Isfahan, Kerman, Bandar Abbas, and Hamadan** (3000 volunteers each).

1. In **Babol and Sari**, all the volunteers will get routine screening and blood draws on Days 0 and 56. A random subset of 900 volunteers (30%) will get an additional serology test on Days 5 and 28.

2. In **Isfahan, Kerman, Bandar Abbas, and Hamadan**, all the volunteers will get routine screening and blood draws without serology tests.

**C2: Two-dose of SOBERANA-02 + third dose of SOBERANA-plus (Days 0, 28, & 56):** We will recruit a total sample size of 6,000 volunteers in two cities of **Zanjan and Yazd** (3,000 volunteers each).

1. **Zanjan:** All the volunteers will get routine screening and blood draws during the study. A random subset of 2,000 volunteers will get additional serologic tests on days 0 and 84 (1 month after the third dose)

2. **Yazd:** All the volunteers will get routine screening and blood draws without serology tests.

**Outcomes**

**Primary Outcome**

Outcome	Definition	Measurement method	Timing of measurement
Symptomatic COVID-19-19 infection	Identification of SARS-CoV-2 RNA (two viral gene targets) in the respiratory samples of suspected cases	Real-time PCR	
C1: From day 14th after the 2nd dose until the end of efficacy study time
 
C2: From day 14th after the 3rd dose until the end of efficacy study time

## Secondary outcomes

Outcome	Definition	Measurement method	Timing of measurement
Severe COVID-19 infection	Includes severe, critical or hospitalized COVID-19 cases	Included those COVID-19 patients with O 2 saturation level $\leq 90\%$ , evidence of lower respiratory disease (e.g., shortness of breath, chest pain or chest tightness) with or without fever $\geq 38^{\circ}\text{C}$ during clinical assessment or imaging, tachypnea (i.e., respiration rate $>30$ breaths/min), increased P(A-a) O 2 gradient, lung infiltration $>50\%$ in CT-scans, PaO 2 /FiO 2 $<300$ mmHg, or acute worsening of respiratory symptoms especially dyspnea, respiratory failure, septic shock, and/or multiple organ dysfunction, hospitalization or death due to COVID-19.	
C1: From day 14th after the 2nd dose until the end of efficacy study time
 
C2: From day 14th after the 3rd dose until the end of efficacy study time

COVID-19-related death	Based on the WHO definition: The death of a COVID-19 case is not attributable to another cause (e.g., trauma). There should not be a recovery interval between COVID-19 infection and death	Based on the diagnosis of PI and Co-PIs in the cities and approval of DSMB	
Humoral immunity	At least a 4-fold rise in Anti-S1 IgG titer in serum sample compared to the baseline	ELISA	28 days month after the last vaccine shot compared to the serum titer of Day 0
Virus neutralization	Detection of antibodies which can inhibit virus replication (an antibody, which can neutralize virus infectivity)	VNT (Virus Neutralization Test)	On days 0 and 28 days after the second dose, serum samples will be taken from a subset of antibody-positive volunteers and the neutralizing antibody titer will be determined

Cell-mediated immunity (CMI)	Measuring Interferon Gamma secreted from PBMC (peripheral blood cells mononuclear cell)	Interferon Gamma Release Assay (IGRA)	In the cities of Babol and Sari, CMI will be performed
Safety	Frequency of local and systemic adverse events disaggregated by intensity (degree) and seriousness (type)	Case investigation form, Diary form, telephonic follow-up	From day 0 until 5 months after the last dose

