### **2. Secondary Objectives**

- o To determine the efficacy of protein conjugated vaccine/ protein conjugated vaccine + third dose to prevent severe forms of COVID-19 in 18–80-year-old Iranians.
- o To determine the efficacy of protein conjugated vaccine/ protein conjugated vaccine + third dose to prevent COVID-19-related death in 18–80-year-old Iranians.
- o To determine the immunogenicity of protein conjugated vaccine/ protein conjugated vaccine + third dose in the 18–80-year-old Iranians.
- o To determine the safety of protein conjugated vaccine/ protein conjugated vaccine + third dose in 18–80-year-old Iranians.

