## **C2: Three-dose Scheme**

Intervention group: Intramuscular injection (Deltoid muscle) of 25 µg SOBERANA-02 vaccine on days 0 and 28 as well as a third dose with SOBERANA-plus on day 56

Placebo group: Intramuscular injection of placebo on days 0, 28 and 56

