#### **4.2 Immunogenicity Assessment**

To assess humoral immunity, Anti-S1(including RBD) IgG antibodies will be measured by ELISA in a subgroup of volunteers in Babol and Sari (C1) and Zanjan (C2) before the first dose and 28 days after the last dose. In addition, on Days 5 and 28, an extra antibody measurement will be done on a random subset of 900 volunteers in Babol and Sari (30% of volunteers in these cities). Limiting these extra measurements in two cities is to minimize the blood sampling and ease the logistic issues. Neutralizing antibodies will be measured by the Virus Neutralization test (VNT) in a proposition of participants (100 individuals).

To assess Cell-Mediated Immunity (CMI), Interferon Gamma Release Assay (IGRA) will be performed on at least 130 participants from Babol or Sari.

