## The timetable of study activities

**Table 1. Timing of activities in Cohort 1 (2-dose scheme)**

No. of visit	1	2	3	4		
Objective of visit	Screening Dose 1, Blood sampling §	Blood sampling from a subset of subjects§	Blood sampling from a subset of subjects §	Blood sampling §	End of monitoring efficacy	End of monitoring adverse events
Month	Month 1			Month 2	Month 4	Month 6
Day	0	5	28	56		
Acceptable interval (open window period) 		+ 2	+ 7	+ 7		
Informed consent Complete eCRF (demographic info, concurrent treatments, history of underlying conditions, etc.)	•					
Blood sampling to assess the previous infection of COVID-19 (antibody assay)	•					
Physical examination 	•		•			
Randomization	•					
Intervention						
Vaccine injection and active monitoring for 0.5 hours after the shot	•		•			
Evaluation of vaccine efficacy						
Monitoring of symptomatic COVID-19 cases (ex-program visit) 	•					
Blood sampling	•			•		
Safety evaluation						
Handover of diary form to volunteers 	•		•			

Returning and reviewing of Diary form			•	•		
Recording adverse event	•					
Recording AEs which need medical intervention and those end up with study stop Recording those interventions (treatments) for AEs	•					
Recording SAEs and their related treatments	•					
Recording other treatments and vaccines during the study period 	•					

§ Among cities under the two-dose scheme (Cohort), just Sari and Babol will do serologic assays for all volunteers on days 0 and 56 and 30% of subjects on day 5 and another 30% on day 28.

1) Window period means an acceptable interval that a volunteer can come for a visit or to receive the intervention

2) A comprehensive physical examination encompasses measuring vital signs, height and weight on day 0. Before every vaccine shot, the volunteer's arm is inspected for regional lymph nodes. Every significant physical finding must be reported as a side event that needs medical intervention. Vital signs will be assessed before vaccination on days 0 and 28. Febrile subjects on day 0 (the 1st dose of vaccine) will be excluded (a temperature beyond 38°C is defined as fever). Those volunteers having fever on day 28 (the 2nd dose of vaccine) will be rescheduled for an alternative date (within the window period) to get their 2nd shot.

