**Table 2. Timing of activities in C2 (3-dose regimen)**

No. of visit	1	2	3	4		
Objective of visit	Screening Dose 1 Blood sampling from 2000 subjects of Zanjan city §	Dose 2	Dose 3	Blood sampling from 2000 subjects of Zanjan city §	End of monitoring efficacy	End of monitoring adverse events
Month	Month 1		Month 2	Month 3	Month 5	Month 7
Day	0	28	56	84		
Acceptable interval (open window period) 	0	+ 7	+ 7	+ 7		
Informed consent Complete eCRF (demographic info, concurrent treatments, history of underlying conditions, etc.)	•					
Blood sampling to assess the previous infection of COVID-19 (Antibody assay)	•					
Physical examination 	•	•	•			
Randomization	•					
Intervention						
Vaccine injection and active monitoring for 0.5 hours after the shot	•	•	•			
Evaluation of vaccine efficacy						
Monitoring of symptomatic COVID-19 (ex-program visit) 	•					
Blood sampling 	•			•		

Safety evaluation						
Handover of diary form to volunteers 	●	●	●			
Returning and review of Diary form 		●	●	●		
Recording adverse event	●					
Recording AEs which need medical intervention and those end up with study stop Recording those interventions (treatments) for AEs 	●					
Recording SAEs and their related treatments 	●					
Recording other treatments and vaccines during the study period 	●					

§ Two cities of Zanjan and Yazd follow the three-dose scheme. Just in Zanjan city, blood samples will be taken for serologic assays from 2000 volunteers on days 0 and 84.

- 1) Window period means an acceptable interval that a volunteer can come for visit or to receive the intervention
- 2) A comprehensive physical examination encompasses the measurement of vital signs, height and weight on day 0. Before every vaccine shot, the volunteer's arm is inspected for regional lymph nodes. Every significant physical finding must be reported as a side event that needs medical intervention. Vital signs will be assessed before vaccination on days 0, 28 and 56. Febrile subjects on day 0 (the 1st dose of vaccine) will be excluded (a temperature beyond 38oC is defined as fever). Those volunteers having fever on days 28 and 56 (the 2nd dose of vaccine) reschedule for an alternative date (within the window period) to get their 2nd and 3rd shots.

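### The virus neutralisation outcome is restricted to antibody-positive volunteers and timed from the second dose, which does not fit the planned placebo comparison and leaves the three-dose cohort without a post-regimen neutralisation result

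*Protocol*

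**What the plan says.** The Secondary outcomes table is the only place in the protocol that fixes who is sampled for VNT and when: "On days 0 and 28 days after the second dose, serum samples will be taken from a subset of antibody-positive volunteers". It does not say at which time point a volunteer must be antibody-positive.

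Section 4.2 gives the number: "Neutralizing antibodies will be measured by the Virus Neutralization test (VNT) in a proposition of participants (100 individuals"). It names no cohort, arm split or selection rule.

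Section 6.2.2 sets the analysis: "seroconversion and neutralization, will be measured in those subjects receiving all vaccine doses and compared with the placebo group".

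The immunogenicity objective covers both regimens: "To determine the immunogenicity of protein conjugated vaccine/ protein conjugated vaccine + third dose in the 18–80-year-old Iranians".

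The C2 intervention group receives "25 µg SOBERANA-02 vaccine on days 0 and 28 as well as a third dose with SOBERANA-plus on day 56". On serology in C2, Table 2 states: "Just in Zanjan city, blood samples will be taken for serologic assays from 2000 volunteers on days 0 and 84". In cohort 1 (C1), Table 1 states that "just Sari and Babol will do serologic assays for all volunteers on days 0 and 56".

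The ELISA outcome in the same secondary outcomes table is timed from the last dose, not from the second.

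**The concern.** There are two separate problems.

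**Selection.** A comparison with placebo is protected by randomisation only if participants enter it without regard to anything the vaccine can change. Antibody status after dosing is exactly what the vaccine is meant to change. The placebo contains no antigen (Annexe 3), so a placebo recipient who is antibody-positive has, false positives and outside vaccination apart, been infected. Such people can be enrolled: section 2.3 excludes current COVID-19, not past infection. Selecting positives in both arms would set vaccine responders against infected people and drop the non-responders.

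**Timing.** The objective includes the regimen with the third dose, and section 6.2.2 refers to all doses. A sample timed from dose 2 cannot describe the completed three-dose regimen.

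At stake is the interpretation of one named secondary outcome, and whether any neutralisation statement can be made for C2. Neither fault can be repaired at the analysis stage if the sera were never selected for assay.

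**Working it through.** The protocol gives no derivation for the 100 VNT participants, so there is no figure to reproduce.

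**1. Day arithmetic**

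| | C1 | C2 |
|---|---|---|
| Dose days | 0, 28 | 0, 28, 56 |
| 28 days after dose 2 | 28 + 28 = 56 | 28 + 28 = 56 (day of dose 3) |
| 28 days after last dose | 28 + 28 = 56 | 56 + 28 = 84 |
| Scheduled serology | 0 and 56 for all volunteers in Babol and Sari (subsets also on 5 and 28) | 0 and 84, Zanjan only |

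The VNT time point fits C1. In C2 it falls on the day of dose 3, when Table 2 and Box 1 list no serology. The ELISA time point fits a scheduled draw in both cohorts.

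**2. Positivity judged after dosing: number of placebo samples**

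Let p_v and p_p be the proportions antibody-positive on vaccine and placebo. The protocol states neither, so both are assumptions. With 4:1 allocation (section 2.1), a random 100 would hold about 80 vaccine and 20 placebo. Among positives,

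placebo share = 0.2·p_p / (0.8·p_v + 0.2·p_p).

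- p_v = 0.90, p_p = 0.10: 0.02 / 0.74 = 2.7%
- p_v = 0.80, p_p = 0.25: 0.05 / 0.69 = 7.2%
- p_v = 0.60, p_p = 0.50: 0.10 / 0.58 = 17.2%

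So about 3 to 17 placebo samples instead of 20.

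**3. Positivity judged after dosing: effect on the contrast**

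Assume a proportion q of positives neutralise, the same in both arms, and no negatives do. The randomised difference is q·(p_v − p_p). Among positives only it is q − q = 0.

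| p_v | p_p | q | Randomised contrast | Among positives |
|---|---|---|---|---|
| 0.60 | 0.40 | 0.60 | 36% vs 24%: 12 points | 0 |
| 0.80 | 0.25 | 0.80 | 64% vs 20%: 44 points | 0 |
| 0.90 | 0.10 | 0.80 | 72% vs 8%: 64 points | 0 |

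If q differed between arms, the contrast among positives would be q_v − q_p. It would no longer depend on how many vaccinees responded.

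**4. Positivity judged at day 0**

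Selection is then on a pre-dose characteristic. Expected positivity is the same in both arms, the 4:1 split is kept and the arms remain comparable. The result describes only volunteers who were seropositive before vaccination, whereas the objective concerns 18–80-year-old Iranians without that restriction.

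**The case against.** **The bias depends on an unresolved reading.** Tables 1 and 2 schedule a day-0 antibody assay to assess previous infection, and the VNT row lists day 0 as a sampling day, so a baseline meaning is possible. This stands: the bias can be stated only conditionally. The baseline reading exchanges bias for a restricted population, so it still does not deliver the comparison that section 6.2.2 describes in the population of the objective.

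**VNT may be meant for C1 only.** Its days match the C1 draws in Babol and Sari, and the other specialised assay, the interferon gamma release assay, is confined to those cities. That is plausible, and leaving C2 out of a 100-person assay could be a deliberate choice. But the protocol does not say so, and section 6.2.2's reference to all doses sits badly with it.

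**The three-dose regimen is never assessed.** A reader might infer this from the timing, but it goes too far. Anti-S1 IgG is measured in 2,000 Zanjan volunteers on days 0 and 84. Only neutralisation is missing after the third dose, so the immunogenicity objective is partly met in C2.

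**The selection would reverse the apparent effect.** A reader might also infer this, because infected placebo recipients could neutralise more often than vaccinees. The documents give no neutralisation rates. Any reversal follows from the two rates one chooses to assume.

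**The consequence is limited.** VNT is one secondary outcome in 100 of 24,000 participants, and the ELISA comparison is not restricted by antibody status. This is correct and limits the weight of the point.

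**Conclusion.** The point holds as a conflict between the VNT sampling rule on one side and the planned analysis and objective on the other.

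- With positivity judged after dosing, the comparison with placebo is biased. Under the assumptions in the working (equal neutralisation among positives, none among negatives), true differences of 12 to 64 points become zero and about 3 to 17 placebo samples remain instead of 20. These are illustrations. Neither the size nor the direction of the bias can be computed from the protocol.
- With positivity judged at day 0, there is no between-arm bias, but the result is confined to previously seropositive volunteers.
- On either reading, C2 has no neutralisation sample after the third dose, and the stated time point has no scheduled C2 serology draw. This part rests on the protocol's own days and needs no assumption.

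The primary outcome and the ELISA outcome are unaffected. The change should be made, because the protocol itself fixes the sampling rule.

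**What to change.** In the Secondary outcomes table, replace the antibody-positive restriction with a random selection of VNT participants within arm from the serology participants, irrespective of antibody status. Test sera from day 0 and 28 days after the last dose (day 56 in Babol and Sari for C1, day 84 in Zanjan for C2), in line with the ELISA outcome. Bring sections 4.2 and 6.2.2 into agreement, and state the number per cohort and arm. If VNT is meant for C1 only, say so and claim no neutralisation result for the three-dose regimen.

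Costs:

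- No extra visits, since these draws are already scheduled, but enough serum must be kept from them. The protocol does not mention storage.
- Some assays are spent on antibody-negative sera.
- Precision falls if 100 participants cover two cohorts. An even split gives 50 per cohort, or 40 vaccine and 10 placebo each at 4:1. A split by cohort size (18,000 to 6,000, or 3:1) gives C2 25 participants, or 20 and 5. The sponsor must accept this, raise the number, or limit VNT to one cohort.
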